17 Central venous to arterial CO₂ partial pressure difference (AVCO₂) measures the circulatory clearance of
18 tissue CO₂ and has been proven to be correlated with CO in critically ill adult patients⁵. Widening of AVCO₂
19 represents an imbalance between CO₂ clearance by CO and tissue CO₂ production. With limited data available,
20 it remains unknown whether AVCO₂ is a useful adjunctive marker for assessment CO adequacy in pediatric
21 patients after cardiac surgery with CPB.

22 Additionally, increase cytokine production both pro- (interleukin (IL)-6, IL-8, and tumor necrotic factor
23 (TNF)- α) and anti-inflammatory cytokines (IL-4, IL-10) caused by CPB-induced inflammatory activation can
24 alter multiorgan function and vascular permeability. The relationship between level of these cytokines and
25 clinical outcomes also remains uncertainty in children population.

26 We aimed to evaluate the association between AVCO₂ and inflammatory markers at 4 different time points
27 post operatively with LCOS-related poor outcome and calculate predictability of these markers to facilitate
28 earlier recognition and management LCOS in children undergone cardiac surgery with CPB.

29 30 7. Objective(s) of the study

31 **Main or Primary objective:** To compare accuracy of prediction of LCOS-related poor outcome between
32 AVCO₂ and traditional bedside surrogates (lactate, ScvO₂ and AVO₂) in children with cardiac disease who
33 undergone CPB.

[figure not shown]
34 **Secondary objectives:**

1 7.1 To evaluate association between AVCO_2 in children with cardiac disease who undergone CPB and other
 2 morbidities: 28-ventilator free day, 28-ICU free day, acute kidney injury, and deaths from any cause during
 3 hospitalization.

4 7.2 To evaluate association between level of pro- and anti-inflammatory cytokine in children who underwent
 5 CPB and LCOS-related poor outcome.

6

7 **8. Conceptual framework**

8

9 **9. Literature review**

10 AVCO_2 difference

11 A retrospective study done by Rhodes LA, et al³ evaluated correlation of AVCO_2 with other cardiac output
 12 surrogates (lactate, ScvO₂ and AVO₂) and its capacity to predict poor outcomes associated with LCOS in 139
 13 infants who underwent CPB. There were only 24.5% of poor outcome in this study. The results showed moderate
 14 correlation between AVCO_2 difference with AVO₂ ($R^2 = 0.53$; $p < 0.01$), and ScvO₂ ($R^2 = -0.43$; $p < 0.01$), but not

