 15 lactate. Unadjusted ROC analysis demonstrated that AVCO_2 had lower AUC than ScvO₂, but higher AUC than
 16 serum lactate (AUC of AVCO_2 0.69 vs ScvO₂ 0.74 vs lactate 0.64). After multivariable logistic regression analysis,
 17 admission AVCO_2 remained significantly associated with poor outcome (OR, 1.3; 95% CI, 1.1-1.45), including
 18 independent association with mortality (OR, 1.2; 95% CI, 1.07-1.31). Limitation of this study include missing data
 19 of blood gas analysis and lack of simultaneous hemodynamic variables and concurrent echocardiogram. The
 20 population in this study also limited only to infant age less than 90 days. Another retrospective cohort study done
 21 in 54 Pakistan's children also showed moderate correlation between AVCO_2 and ScvO₂ ($R^2 = 0.34$), but the
 22 participants were still limited in complete repair of congenital heart defect. As accuracy of ScvO₂ depends on
 23 intracardiac structure, the correlation between AVCO_2 and ScvO₂ in incomplete repair is unknown⁶.

1 A retrospective study done by Arkamatsu T, et al⁷ evaluated the association of AVCO₂ with morbidities in 114
2 pediatrics patients who undergone CPB. The result reported poor correlation of AVCO₂ with other parameters
3 (lactate, ScvO₂). Additionally, comparing patients who had high (VACO₂ > 6 mmHg) and low gap (VACO₂ < 6
4 mmHg) of VACO₂, there was no difference of intubation time nor length of ICU stay. However, the outcome in this
5 study did not directly relate to LCOS.

6

7 There were 2 prospective and 4 retrospective studies done in adult who undergone CPB^{4, 8-12}. Some reported
8 the significant association between AVCO₂ and poor outcome^{4, 9-11} but some did not^{8, 12}. However, poor outcome
9 was defined differently in each study which might not be referred to LCOS-related complications.

10 **Inflammatory cytokines**

11 Unlike the AVCO₂ studies, most studies on inflammatory cytokine in pediatric cardiopulmonary bypass surgery
12 were prospective analysis. Allan CK, et al¹³ assessed the relationship between level of inflammatory cytokines (IL-
13 6, IL-8, IL-10, TNF α , IL-1 β , and CPR) and clinical outcome at different time points (pre CPB, post CPB at 0, 6
14 12, and 24 hours) in 93 pediatric patients. The result demonstrated that level of postoperative IL-6 and IL-8 at 0
15 and 24 hours correlated significantly with length of ICU stay and postoperative blood product administration.

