15	Where: Sensitivity (p)	= 0.85
16	Precision (d); not more than 10% of p	= 0.09
17	Alpha	= 0.05

18 We applied the sensitivity of lactate > 3 mmol/L for major morbidity, which defined as at least one of
19 complications (i.e., neurological, pulmonary, gastroenteric, and need for extracorporeal membranes oxygenation or
20 ventricular-assist device, or sepsis)¹⁶.

21 Estimated patient (n_0) is 61 cases. Based on 48% of incidence of LCOS-related outcome last year in our
22 study setting, the required total sample size including non-disease and disease participants will be 128 (=61/0.48).

23 Regarding with our sample size calculation for two objectives and an estimate of 20% of unusable data
24 from a sample of 128 participants has been considered. The final sample size is 154 participants for sensitivity of
25 0.85. However, we will collect blood sample for inflammatory markers in 32 patients for preliminary analysis.

26 **9.6. Variables of the study**

27 9.6.1. Dependent variable: poor outcomes indirectly represented from low cardio output syndrome

28 - LCOS-related poor outcome is modified from the study of Drennan SE, et al and Carmona, et al^{14, 15}
29 which consisting of at least two of the following criteria within 48 hour post operatively:

- 1 a. Clinical findings suggestive of LCOS: prolonged capillary refill > 3 s, systolic blood pressure < 5th
2 percentile for age and gender, persistently elevate of LA pressure above 10 mmHg for at least 6 hr
3 , low urine output (< 1mL/kg/hr) for at least 6 hour despite diuretic use
- 4 b. Laboratory findings suggestive of LCOS: persistently elevated lactate (>2 mmol/L), metabolic
5 acidosis with an increase in the base deficit (>4 mmol/L) for at least 6 hr consecutively.
- 6 c. Vasoactive-inotropic score (VIS) \square 20
- 7 d. Any unplanned surgical reinterventions, cardiac arrest, or utilization of extracorporeal membrane
8 oxygenator (ECMO) within 48 hours
- 9 e. Left ventricular fraction less than 50% by echocardiography

10 The LCOS-related outcome will include both anatomical LCOS and physiological LCOS that caused by

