3. Preoperative blood sample 1.5 mL will be collected for inflammatory markers level at the same time when patient has intravenous access preparing for NPO or other preoperative blood sample.

4. Patient goes on open heart cardiac surgery and will be admitted directly to pediatric intensive care unit (PICU) for postoperative care.

5. Blood sample for blood gas 0.3 mL for each central line catheter and arterial line catheter and inflammatory markers 1.5 mL drawn from arterial line will be collected at 0, 6, 12, and 24 hours after PICU arrival. Arterial and venous blood gas are accepted if samples are collected within 5 minutes of each other. We allow time gap for collecting blood +/- 1 hr from schedule due to unpredictable ICU occupy.

6. Attending physician provides standard care for post cardiac operation. The decision of treatment by attending physician will not be involved by researchers. Inflammatory markers results will be reported after patient is discharged from hospital to minimize influence of result to physician's decision on treatment.

1 7. Cardiologist will perform echocardiography to evaluate left ventricular function and anatomical defect
 2 that could mimic signs of LCOS within 48 hours postoperatively.

3 8. Researcher prospectively collects postoperative variables including hemodynamic variables and
 4 therapeutic interventions and patient's outcome.

5 9. The primary study endpoint is poor outcome related to LCOS. The secondary endpoints are 28-day
 6 ventilator free day, ICU free day, deaths and correlation of AVCO₂ with other cardiac output surrogates
 7 (AVO₂, ScvO₂ and arterial blood lactate).

8 10. If either central line or arterial line catheter are displaced before 24-hour, remaining data will be
 9 recorded as missing data.

10 **Describe procedures/process of the study. Show how research methodology in the study is different from
 11 the routine practice?**

Processes which are routine practice	Processes which are research
1. Pre-operative lab sampling; CBC, Coagulogram, electrolyte, group match for blood component	1. Adding inflammatory markers to pre-operative lab
2. Serial ABG sampling q 2-6 hr depend on severity of patient	2. Extra 2 blood sampling for VBG (0.3 mL each)
3. Serial VBG sampling q 24 hr	3. Mandatory blood sampling q 6 hr x 5 times for inflammatory markers (1.5 mL each)

12 **9.8. Study instrument(s) and outcome measurement(s)**

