- Blood sample for blood gas analysis 0.3 mL will be drawn from arterial line and central venous catheter each with different time less than 5 minutes. The arterial and venous gas will be analyzed by ABL800 Basic (Radiometer, Copenhagen, Denmark) which is located in PICU
- Blood sample for inflammatory markers 1.5 mL will be collected into 3 mL vacutainers without anticoagulant. Collected blood will be kept on room temperature and sent to division of immunology and virology within 3 hours after collecting. Samples will be centrifuged at 500 x g for 15 minutes at 4°C. Supernatant will be transferred to a clean polypropylene tube. Separated serum will be aliquoted into cryogenic vial and stored at -80°C until analysis.
- Serum cytokines (TNFα, IL-1β, IL-6, IL-8, IL-10) will be quantified in serum using multiplex immunoassays (Bio-Plex Pro Human Screening Panel 5plex XPLEX, Bio-Rad, California, USA). The plate will be read on Bio-Plex®200 array reader (Bio-Rad, California, USA) and analyzed using Bio-Plex Manager™ software. Sample will be run in duplicates and cytokine level will be quantified via comparison to standard curve.

1 **9.9. Data collection methodology**

2 - Data record form consists of 5 parts: patient's profile, characteristic of cardiac disease, intra- and post-
3 operative intervention, laboratory values at 4 different time points, and PICU outcome. Researcher will
4 collect data via electronic medical records, nursing record form, and blood gas record sheet of each
5 participant.

6 **9.10. Data management**

7 - All of data will be collected in record form before putting in Epidata program. Study codes will be used on data
8 collection and data document instead of hospital number of patients.

9 **9.11. Statistical analysis**

10 Descriptive part:

11 - For continuous data (i.e., AVCO₂, ScvO₂, lactate, inflammatory markers, and others), we will use mean
12 (\pm SD) in normal distribution and median (\pm IQR) in non-normal distribution. We will use percentages for
13 categorical data (i.e., LCOS-related poor outcome).

14 Analytic part:

15 - Two means of the continuous outcomes will be compared using t-test or Mann Whitney U test. Two or
16 more proportions of the categorical outcomes will be compared using Chi-square or Fisher-exact test.
17 - We will apply the pairwise correlation analysis among independent variables: AVCO₂, lactate, ScvO₂,
18 inflammatory markers with time lagged factor.

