19 - For primary objective, we will calculate and compare the accuracy of prediction of LCOS-related poor
20 outcome between AVCO₂ and traditional bedside surrogates, using diagnostic test indices (i.e., sensitivity,
21 specificity, predictive values).
22 - According to secondary objectives, Cox proportional hazard model will be conducted to examine the
23 association between LCOS-related outcomes and other variables. Potential confounders (i.e., age, gender,
24 RACHS score, nutritional status, duration of bypass time or aortic clamp time) were included in the initial
25 model. Then, backward stepwise refinement was performed. Statistical significance was considered when
26 the p-value is less than 0.05.
27 - Area under the Receiver Operating Characteristic (ROC) to evaluate predictability of AVCO₂ compare with
28 other parameters.
29 - Sensitivity analysis in patient who has physiological LCOS-related outcome.
30 - Subgroup analysis between children who undergone univentricular repair and biventricular repair

32 **10. Ethical consideration**

33 **10.1. Possible risks/effects in the study, including preventive and alleviation measures**

34 - According to protocol of this study, the patients might be at risk of infection from collecting blood from
35 arterial line and central venous catheter. However, expertise ICU nurses practically perform blood

1 collection in sterile technique. If patient develops catheter-related blood stream infection, empirical
2 antibiotics will be given immediately.

3 - Patient will be at risk of anemia. According to Ethics committee guideline, amount of blood drawn from
4 patient will not be over the maximum volume for patient's body weight and patient's Hb must be more
5 than 10 g/dL at the time of blood drawing. Packed red cell will be given if patient's Hb is less than 10
6 g/dL in standard care

7 **10.2. Describe the process/ system for assuring confidentiality and the privacy of the research
8 participants/communities**

9 Study codes will be used on data collection and data document instead of hospital number. Subject
10 information will be stored securely in the computer and only researcher can access through data.

11 **10.3. Benefits of the study for participants and the community/country including how findings of the
12 study use for strengthening community.**

13 Since there are limitation of using traditional bedside surrogates (serum lactate, ScvO₂ and AVO₂) to

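### The primary comparison of AVCO₂ with lactate, ScvO₂ and AVO₂ has no fixed index, time, cut-off, paired method or multiplicity rule, and the lactate contrast is partly biased because lactate is part of the outcome

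*Combined protocol and SAP*

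**What the plan says.** Section 7 makes the primary objective a comparison of predictive accuracy: AVCO₂ against lactate, ScvO₂ and AVO₂. Under 9.7, step 5, the blood samples "will be collected at 0, 6, 12, and 24 hours after PICU arrival".

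Section 9.11 has three lines that bear on this comparison:

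- The primary line compares accuracy for the poor "outcome between AVCO₂ and traditional bedside surrogates, using diagnostic test indices (i.e., sensitivity", specificity and predictive values). It names no test.
- A separate line reads "Area under the Receiver Operating Characteristic (ROC) to evaluate predictability of AVCO₂ compare with" other parameters. It is not marked as primary and names no method for correlated curves.
- A general line says two or "more proportions of the categorical outcomes will be compared using Chi-square or Fisher-exact test". The primary line does not refer to it.

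The outcome in 9.6.1 requires at least two of criteria a to e within 48 hours. Criterion b begins "Laboratory findings suggestive of LCOS: persistently elevated lactate (>2 mmol/L), metabolic" and continues with acidosis and a raised base deficit. Whether its two elements are joined by *and* or *or* is not stated. The only sensitivity analysis in 9.11 concerns physiological LCOS; no analysis takes lactate out of the outcome.

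Section 9.5 sizes the study for a sensitivity of 0.85 with precision 0.09. AVO₂ is a comparator in section 7 but is missing from the variable list in 9.6.2 and from the correlation list in 9.11.

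**The concern.** There are two separate problems.

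**Missing prespecification.** Three comparators at four times give 12 contrasts for each index, and sensitivity, specificity, two predictive values and AUC are all available. Sensitivity cannot be computed without a cut-off, and 9.11 gives none. The lactate limit of 3 mmol/L appears only as the source of the sample-size assumption, and the 6 mmHg CO₂ gap only in the literature review. The most favourable time, index and cut-off could therefore be chosen after the data are seen. The markers are also measured in the same child, so a valid comparison has to allow for the pairing.

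**Lactate on both sides.** Lactate is an index test and also helps to define the outcome; AVCO₂ does not. Lactate can then look better than AVCO₂ partly by construction, which works against the marker under study.

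Because the sample was not sized for a difference between markers, a non-significant result could also be misread as showing that AVCO₂ is as good.

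**Working it through.** **1. The plan's own figure (9.5).** n₀ = 1.96² × 0.85 × 0.15 / 0.09² = 60.5, so 61 cases. Then 61/0.48 = 127.1, so 128; and 128 × 1.2 = 153.6, so 154. Check: 1.96 × √(0.85 × 0.15/61) = 0.090. The calculation reproduces, for one sensitivity. Losing 20% of 154 leaves 154 × 0.8 = 123 children, of whom 123 × 0.48 = 59 are cases. The usable range is thus 59 cases and 64 non-cases up to 61 and 67.

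**2. Detectable paired AUC difference.** As illustration, take the AUCs that the literature review gives for one infant study: "serum lactate (AUC of AVCO_2 0.69 vs ScvO₂ 0.74 vs lactate 0.64". The Hanley-McNeil variance for m cases and n non-cases is

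SE² = [A(1−A) + (m−1)(Q₁−A²) + (n−1)(Q₂−A²)]/(mn), with Q₁ = A/(2−A) and Q₂ = 2A²/(1+A).

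For A = 0.69, m = 61, n = 67: [0.2139 + 60 × 0.0506 + 66 × 0.0873]/4087 = 0.00221, so SE = 0.0470. Likewise SE = 0.0490 at 0.64 and 0.0442 at 0.74.

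The SE of the difference is √(SE₁² + SE₂² − 2r·SE₁·SE₂), where r is the correlation between the two AUC estimates. The documents do not give r, so 0 to 0.7 is assumed. The multiplier for 80% power is 1.960 + 0.842 = 2.802 at 0.05, and 3.236 at 0.05/3, the first Holm step.

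| r | SE, 0.69 vs 0.64 | Detectable (first Holm step) | SE, 0.69 vs 0.74 | Detectable (first Holm step) |
|---|---|---|---|---|
| 0 | 0.0679 | 0.190 (0.220) | 0.0645 | 0.181 (0.209) |
| 0.3 | 0.0568 | 0.159 (0.184) | 0.0540 | 0.151 (0.175) |
| 0.5 | 0.0480 | 0.135 (0.155) | 0.0456 | 0.128 (0.148) |
| 0.7 | 0.0372 | 0.104 (0.120) | 0.0354 | 0.099 (0.115) |

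With 59 and 64 the ranges are 0.101 to 0.194 and 0.117 to 0.224. Power at 0.05 for a gap of 0.05, the size seen in that infant study, is 11% to 29% (61 and 67).

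**3. Lactate artefact (simulation; every setting is an assumption).** Two markers were given the same relation to a latent severity (loading 0.4 to 0.6). The other criteria loaded 0.6 to 0.8, measured and persistent lactate correlated 0.5 to 0.9, and the lactate component was present in 30% to 50%. The outcome was at least two of five criteria, at 48% incidence. Lactate's AUC minus AVCO₂'s AUC was then:

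| Outcome used | AUC advantage of lactate |
|---|---|
| As planned | about 0.01 to 0.10 |
| Lactate removed from b, base deficit kept, acidosis and lactate correlated 0.3 to 0.7 beyond severity | about 0.01 to 0.06 |
| Whole of criterion b removed | within about 0.005 of zero |

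Other settings gave values as low as 0.003 and, where b was lactate alone, as high as 0.13. The artefact vanished only when measured and persistent lactate were assumed unrelated beyond severity, which is not plausible within one child.

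**4. Timing.** Section 6 places LCOS commonly at 6 to 18 hours after ICU admission. Of the sampling times, 0 h lies before that range, 6 h at its start, 12 h inside it and 24 h after it. A contrast at 12 or 24 h can follow onset, and so would not test prediction.

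**The case against.** The comparators are named in section 7, and the ROC line needs no cut-off and fits the primary objective, since objectives 7.1 and 7.2 concern association only. That stands: what is missing is a single primary index and time and a paired method, not the idea of the comparison. The proposed fix builds on the ROC line.

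Several stronger readings are tempting, but the documents do not support them:

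- *The plan will compare paired sensitivities by chi-square and lose power.* The general line names chi-square and Fisher, but the primary line does not call on them.
- *The false-positive rate is 46%.* That is 1 − 0.95¹² = 0.46, for 12 independent tests each at 0.05. The plan does not say it will run them, and correlated tests would give less. It shows only what could happen.
- *The lactate comparison is circular.* Lactate is part of one of five criteria and two are needed, so the overlap is partial.
- *The sample size is wrong.* Section 9.5 does what it says; it answers a different question.
- *The detectable difference can be stated for each comparator.* One cited study is summarised as showing no correlation of AVCO₂ with lactate, which is not a correlation of zero. For another, "The result reported poor correlation of AVCO₂ with other parameters", ScvO₂ included. These summaries do not fix r for any one comparator.
- *Taking out only the lactate element cures the bias.* This holds only if base deficit is unrelated to lactate once severity is allowed for.

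Holm's method is one defensible multiplicity rule among several.

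**Conclusion.** The concern holds in two parts. First, the primary comparison lacks a primary index and time, cut-offs, a paired method and a multiplicity rule. This follows from the text and rests on no assumption. Second, the lactate contrast as written is partly biased towards lactate, by about 0.01 to 0.10 in AUC under the assumed settings. The size is uncertain. The direction is not, provided that measured and persistent lactate are related within a child. The upper part of that range exceeds the 0.05 gaps in the cited infant study.

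The detectable difference of about 0.10 to 0.19 (0.12 to 0.22 at the first Holm step) rests on the assumed r and on AUCs borrowed from that study. It is a statement of what the sample can show, not an error in 9.5. The changes should be made before outcome data are seen.

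**What to change.** 1. **9.11, primary analysis.** Make the paired AUC difference (DeLong, 95% CI) of AVCO₂ versus each of lactate, ScvO₂ and AVO₂ the primary contrast, at one named time chosen so that the sample normally precedes LCOS onset. Apply Holm over the three comparators, or state another rule. Other times are secondary, as are sensitivity and specificity at prespecified cut-offs (McNemar). Predictive values are descriptive.
2. **Lactate.** Base any claim on AVCO₂ versus lactate on the outcome without criterion b (at least two of a, c, d, e), and report the full-outcome result beside it. Removing only the lactate element is at most a sensitivity analysis. State whether lactate and base deficit in criterion b are joined by *and* or *or*.
3. **AVO₂.** Add it to 9.6.2 and to the correlation list in 9.11.
4. **9.5.** State that the size was set for the precision of one sensitivity. State that about 123 to 128 usable children can detect, with 80% power, a paired AUC difference of roughly 0.10 to 0.19 (0.12 to 0.22 at the first Holm step) for r from 0.7 down to 0. Add that non-significance will not be read as equivalence. Give no figures by comparator.

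**Cost.** Wording and standard software; no added patients or samples. Other times lose primary status. Dropping criterion b leaves fewer cases for the lactate contrast: at an assumed incidence of 33% to 46% in 123 children (123 × 0.33 = 41 to 123 × 0.46 = 57 cases), the detectable difference is about 0.11 to 0.21, or 0.12 to 0.24 at the first Holm step.

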21 **3.7 Name:** [name]

22 **Position:** Clinical instructor

23 **Affiliation:** Division of Pediatric Critical Care Medicine, Department of Pediatrics

24 **[contact] **Mobile [contact]

25 **E-mail:** [contact]

26 **Responsibility in the project:** recruit participant, review manuscript

27

28 **4. Student support**

29 **Check ✓ in () that apply**

30 () Not associated

31 (✓) Undergrad./post grad. [name].

32 **5. Keywords:** AVCO₂, inflammatory markers, post cardiac surgery, cardiopulmonary bypass

33 **6. Background and rationale**

34 Cardiopulmonary bypass (CPB) is a potent stimulus causing systemic inflammatory response in children
35 with cardiac disease who undergone open heart surgery. Mechanisms of inflammatory generator during CPB

1 include blood contact with CPB circuit, ischemia-reperfusion injury, heparin-protamine interactions, and surgical
2 trauma. These mechanisms aggravate the activation of complement cascade, release of endotoxin, and altered
3 cytokine production which led to low cardiac output syndrome (LCOS)¹

4 The LCOS refers to declining cardiac function in the face of an elevated demand of cardiac output which
5 may lead to multiorgan failure and death. Incidence of the LCOS is approximately 25% of children after cardiac
6 surgery¹ and commonly occurs 6- 18 hours following admission to intensive care unit². Currently, there is no
7 consensus for diagnostic criteria of the LCOS and accurate detection of early cardiac output (CO) insufficiency
8 is a challenging task especially in post-operative children. Measurement CO by using thermodilution method
9 via Swan-Ganz catheterization or transesophageal echocardiography are not applicable in pediatrics setting
10 meanwhile transthoracic echocardiography immediately after post-cardiac operation is limited due to surgical
11 wound and tissue swelling. In Songklanagarind Hospital, clinicians practically use parameters such as serum
12 lactate, central venous oxygen saturations (ScvO₂), and arteriovenous oxygen difference (AVO₂) as bedside
13 surrogates of CO. However, these parameters can be influenced by multiple factors unrelated to LCOS³.
14 Hyperlactatemia in cardiac surgery could be elevated due to post-operative stress response, use of beta-
15 adrenergic agonist, hyperglycemia, or reduce lactate clearance due to transaminitis while normal values of
16 ScvO₂ can be found despite microcirculatory dysfunction and localized tissue hypoxia⁴.

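### The backward-stepwise Cox model for the secondary objectives does not match a yes/no 48-hour outcome with no defined event time, is fragile in the 32-child cytokine subset, and is not clearly applied to the objective 7.1 outcomes

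*Combined protocol and SAP*

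**What the plan says.** **The model.** Section 9.11 states: "According to secondary objectives, Cox proportional hazard model will be conducted to examine the", continuing "association between LCOS-related outcomes and other variables. Potential confounders (i.e., age, gender". The rest of the confounder list is RACHS score, nutritional status, and bypass or clamp time, which makes five. All enter an initial "model. Then, backward stepwise refinement was performed. Statistical significance was considered when" p is below 0.05.

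**The outcome.** Section 9.6.1 defines the LCOS-related poor outcome as a composite, "which consisting of at least two of the following criteria within 48 hour post operatively". It gives no time origin, onset rule or censoring rule.

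**The cytokine subset (objective 7.2).** Section 9.5 says: "However, we will collect blood sample for inflammatory markers in 32 patients for preliminary analysis". The expected incidence is in the same section: "Based on 48% of incidence of LCOS-related outcome last year in our" setting. Section 9.8 lists five cytokines. Section 9.6.2 gives five sampling times: before surgery and at 0, 6, 12 and 24 hours.

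**Objective 7.1.** AVCO₂ is to be related to "morbidities: 28-ventilator free day, 28-ICU free day, acute kidney injury, and deaths from any cause during" the hospital stay. Section 9.6.1 scores free days as zero in children who die.

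**The concern.** Three things do not fit together.

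- **Model and outcome.** A Cox model needs an event time, and the outcome is defined only as met or not met by 48 hours. Some criteria must persist for 6 hours, and the echocardiogram may be done at any point in the window, so onset is not self-evident. The background says LCOS "commonly occurs 6- 18 hours following admission to intensive care unit". The 6, 12 and 24 hour samples therefore fall inside the event window and may follow onset.
- **Model and subset.** Five confounders plus a cytokine are to be fitted, then reduced stepwise, in 32 children. An unpenalised fit to so few events exceeds its nominal error rate, and selection can drop a real confounder by chance. Repeating this over cytokines and times adds false positives.
- **Model and objective 7.1.** A reader cannot tell whether the associations of AVCO₂ with morbidity will be adjusted, or by what model.

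At stake are misleading cytokine associations and choices about objective 7.1 made after the data are seen. The primary diagnostic comparison is not affected.

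**Working it through.** **1. The plan's own sample size (section 9.5) reproduces.**
- n₀ = 1.96² × 0.85 × 0.15 / 0.09² = 60.5, so 61.
- 61 / 0.48 = 127.1, so 128.
- 128 × 1.2 = 153.6, so 154.

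This sizes the diagnostic objective. No calculation is given for the Cox model or for the 32.

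**2. Events per parameter.** Parameters: 5 confounders (one term each) + 1 cytokine at one time = 6.

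| Children | Expected events | Per parameter |
|---|---|---|
| 32 | 32 × 0.48 = 15.4 | 2.6 |
| 128 | 128 × 0.48 = 61.4 | 10.2 |
| 154 | 154 × 0.48 = 73.9 | 12.3 |

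The binomial 95% range for 32 children at 48% is 10 to 21 events, or 1.7 to 3.5 per parameter. Entering RACHS or nutritional status as categories, for 8 parameters in all, gives 15.4 / 8 = 1.9.

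**3. What this does to the test.** The plan defines no event times, so the simulation assumes exponential times censored at 48 hours. It has five confounders, one of them real (assumed hazard ratio 1.5), and a marker with no effect. r is the assumed correlation of the marker with the real confounder.

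| Analysis, n = 32 | Null rejected, r = 0 | Null rejected, r = 0.5 |
|---|---|---|
| Full Cox, five confounders | about 8-9% | about 9% |
| Cox after backward selection | 8.3-9.6% | about 13-14% |
| Firth logistic, all five kept | about 5% | about 5% |
| Firth logistic, one wrong adjuster | – | about 10% |

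- The full Cox model at n = 154 rejects in about 5.8% of runs (r = 0).
- Null hazard ratios per SD from the full Cox model (middle 95%, r = 0) span 0.45-2.15 at n = 32 and 0.79-1.28 at n = 154.
- At n = 32 and a retention threshold of 0.05, the real confounder is dropped in about 65% of runs. At thresholds of 0.10 and 0.20 this is 52% and 38%. At 0.05 it is about 13% for n = 128 and 8% for n = 154.

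**4. Multiplicity.** 5 cytokines × 5 times = up to 25 tests. If they are independent and each holds 5%, the chance of at least one false positive is 1 − 0.95²⁵ = 0.72. With assumed correlations of 0.5 and 0.8 it is 54% and 30%, or 47% and 24% under a simpler correlation pattern.

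**5. Objective 7.1, places side by side.**
- Section 9.11 names only LCOS-related outcomes for the Cox model, though in the plural and under the secondary objectives.
- Section 9.6.1 defines kidney injury and free days under its dependent-variable heading.
- Section 9.7, step 9, lists free days and deaths as secondary endpoints, separate from the LCOS endpoint.

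If these outcomes are in the Cox model, free days set to zero for deaths are not event times. If they are not, only the unadjusted two-group tests of section 9.11 remain.

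**The case against.** **The cytokine work is labelled preliminary.** True, and this softens the consequence. But section 9.11 exempts it from neither the adjusted model nor the 0.05 threshold, and section 14 plans publication.

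**Onset could be dated.** Arrest, ECMO and reintervention have times, and section 9.7 has haemodynamics and interventions recorded prospectively. A reader might infer that a Cox model cannot be fitted at all. The documents do not support that: what is missing is a definition, and data to build one may exist.

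**A threshold is given.** The sentence after the stepwise step sets p < 0.05. A reader might say the plan has no retention rule. The fair description is that it is ambiguous whether this value governs retention as well as significance.

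**Five adjusters are not the problem.** This stands. With 2.6 events per parameter it is tempting to conclude that five-term adjustment is untenable in 32 children and should be cut to one. The simulation shows otherwise. Penalised logistic regression with all five holds about 5%, while one wrong adjuster gives about 10%. The excess error comes from the unpenalised fit and the selection; five-term adjustment costs only some precision.

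**The full cohort is adequate.** Also true: 10-12 events per parameter. The sparsity is confined to objective 7.2.

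**Conclusion.** The point holds in a limited form. The mismatch between a Cox model and an outcome without an event time rests on the text alone, as does the ambiguity over objective 7.1. The 2.6 events per parameter rests on the plan's 32 and 48%, on that incidence applying to the subset, and on one term per confounder.

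The error rates (about 8-9% for the full Cox model, 13-14% after selection at 0.05) depend on assumed exponential event times. The second also assumes a hazard ratio of 1.5 and a correlation of 0.5. They show direction and rough size and do not predict this study's results.

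Two further readings go too far. The 72% is not a ceiling: it assumes independent tests that each hold 5%, falls with positive correlation, and would rise if each test exceeded 5%. The plan also does not commit to 25 separate models. Nor can it be said that objective 7.1 has no analysis, since the generic two-group tests could be meant for it. What is missing is a clear assignment.

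**What to change.** **Objective 7.2.**
- Replace the stepwise Cox model with a Firth-penalised logistic model of the 48-hour LCOS outcome for each log-transformed cytokine.
- Keep the sponsor's pre-specified confounders in the model without selection; all five can stay.
- State that samples at 6-24 hours may follow LCOS onset.
- Report estimates with confidence intervals as exploratory, and control the false discovery rate over the cytokine-by-time tests.

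**Objective 7.1.**
- State which outcomes are modelled and at which time point AVCO₂ is the exposure.
- Use logistic regression for kidney injury and in-hospital death, penalised if deaths are few, and ordinal or rank-based regression for free days.
- Retain the pre-specified confounders.

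**Cost.** SAP wording and a little analysis work, with these limits:
- *Precision stays poor.* With five adjusters at n = 32, null odds ratios per SD span about 0.4-2.5 (r = 0) or 0.3-3.1 (r = 0.5). With only the right adjuster at r = 0.5 the span is about 0.37-2.6.
- *Power is low.* With one independent adjuster, 80% power needs an odds ratio of about 3.5 per SD at 0.05, and about 9 at the strictest false-discovery step (0.05/25 = 0.002). Five adjusters should not be expected to need less.
- *Deaths may be few.* The documents give no rate. At an assumed 3-10%, the range is 128 × 0.03 = 3.8 to 154 × 0.10 = 15.4 deaths, or 0.6-2.6 per parameter with six terms.
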